	
crossover part of the study will be analyzed by means of proportional hazard time-depended analysis. Median disease-free survival will be calculated with the Kaplan-Meier method.
 
All statistical testing is two-sided at the nominal 5% significance level, with no adjustment for multiplicity. All patients who receive at least one regorafenib plus durvalumab dose will be included in the safety analysis.

Publication plan	
 - Timelines 2025 Q4 - Target Journals: Lancet, Lancet Oncology, JCO.

Table 1. SCREENING PHASE

	28 to 1 day before randomization ^d	
Informed consent	X	
Inclusion / Exclusion criteria	X	
General disease medical history	X	
Prior / Concomitant medications	X	
Complete physical examination	X	
ECOG PS	X	
Weight	X	
Vital Signs ^a	X	
12-lead ECG ^b	X	
Tumor imaging ^c	X	Must be performed within 10 weeks before D1C1. Tumor imaging can be accepted even if performed before the procedures to obtain NED status.
Hematology, chemistry, coagulation and pregnancy test ^d	X	
Biomarkers ^d	X	CEA and CA 19-9 must be on normal range
Histologic Confirmation	X	Only if surgery performed to obtain NED state, resection of the metastases must be R0

Table 2. Experimental arm

	From -7 days to Day 1 Cycle 1	Day 1 Cycle 1	Day 8, 15, 22 Cycle 1	Day 1 Cycle 2	Day 15 Cycle 2	Day 1 Cycle 3 and above up to 1-year (12 cycles)	QW12 from C1D1 (+/- 7 days)	End of treatment visit	Treatment discontinuation 30-days from last treatment or at initiation of other anticancer therapy (whichever occurs first)	Follow-up period ^g
Prior / Concomitant medications								X		X
Complete physical examination								X		X
Limited physical examination ^a		X	X	X	X	X				
ECOG PS		X	X	X	X	X		X		X
Weight		X		X		X				
Vital Signs ^a		X	X	X	X	X		X		X
12-lead ECG ^b								X		

Tumor imaging/ response assessments ^c							X	X		X
Hematology ^d	X		X	X	X	X		X		
Coagulation ^d	X							X		
Chemistry ^d	X		X	X	X	X		X		
Biomarkers ^d							X	X		X
Durvalumab Administration		X ^e		X ^e		X ^f				
Regorafenib Administration		X ^e		X ^e		X ^f				
AEs assessments	X		X	X	X	X		X	X	X
Survival and anti-cancer therapy									X	X

Table 3 - Control arm

	QW12 from C1D1 (+/- 7 days)	End of treatment visit	Treatment discontinuation 30-days from last treatment or at initiation of other anticancer therapy (whichever occurs first)	Follow-up period ^g
Prior / Concomitant medications	X	X		X
Complete physical examination	X	X		X
ECOG PS	X	X		X
Weight	X	X		
Vital Signs ^a	X	X		X

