Tumor imaging/ response assessments ^c	X	X		X
Hematology ^d	X	X		X
Chemistry ^d	X	X		X
Biomarkers ^d	X	X		X
AEs assessments	X	X	X	X
Survival and anti-cancer therapy			X	X

Abbreviation: CBC: cell blood count; RBC: red blood cell; WBC: White blood cell; aPTT: activated partial thromboplastin time; PT: prothrombin time; INR: international normalized ratio; AST: Aspartate aminotransferase; ALT: alanine aminotransferase; LDH: Lactate dehydrogenase; β -hCG: beta-human chorionic gonadotropin; Na: sodium; K: potassium; Cl: chloride; Mg: magnesium; Ca: calcium; P: phosphate; CEA: Carcinoembryonic antigen; Ca 19-9: Carbohydrate antigen 19-9; ECOG PS: Eastern Cooperative Oncology Group Performance Status; ECG: electrocardiogram; AEs: adverse events

a) Vital signs and Physical examination

Patients will have a complete physical exam to include an examination of major body systems and an assessment for emergent toxicities or changes from prior visits. Limited physical examination should be performed symptom-directed.

Examinations will be conducted by a physician, trained physician's assistant, or nurse practitioner, as acceptable according to local regulation.

Vital signs include: blood pressure and heart rate, body temperature, respiratory rate.

b) Electrocardiogram (ECG)

Perform a 12-lead resting electrocardiogram (ECG) before the beginning of the treatment, at the end-of-treatment and if clinically indicated. Patients should be in a supine position for at least 10 min before recording. ECG tracings will be reviewed by a qualified physician for assessment of QT interval as well as signs of qualitative abnormalities, including evaluation of rhythm, ST segment morphology, T wave morphology, and presence/absence of U wave.

The original ECG tracing will be maintained in the source documentation of each patient.

c) Tumor imaging/ response assessments

Including computed tomography (CT) scan / magnetic resonance imaging (MRI) / PET scan. The same radiographic procedure should be used throughout the study for each patient.

Tumor assessment should be performed every 12 weeks \pm 1 week for the first year (relative to the date of randomization), every 16 \pm 1 week in the second year and then every 24 weeks \pm 1 week thereafter until RECIST 1.1-defined radiological PD or death (whichever comes first).

d) Local laboratory assessments will include the following:

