- Hematology profile (CBC, including RBC count, hemoglobin, hematocrit, WBC count with differential [neutrophils, eosinophils, lymphocytes, monocytes, basophils] and platelet count)
- Coagulation profile (aPTT, PT, INR)
- Chemistry profile includes Na, K, Cl, Mg, Ca, P, blood urea nitrogen, creatinine, glucose, total protein, albumin, AST, ALT, alkaline phosphatase, total bilirubin, LDH, amylase, lipase
- Pregnancy test (a positive urine test will be confirmed with a serum pregnancy test) during the study (for woman of childbearing potential). If a patient becomes pregnant while in the study, the study treatment must be immediately discontinued. Pregnancy information for a female patient or for the female partner of a male patient should be reported within 24 hours from the time the Investigator first becomes aware of a pregnancy or its outcome.
- Biomarkers: CEA, Ca19.9, backup plasma sample.

Samples for hematology, serum chemistry, coagulation, pregnancy test and biomarkers will be analyzed at the study site's local laboratory. Investigator may have additional blood tests performed for the purpose of planning treatment administration, dose modification, or following AEs.

Procedure does not have to be repeated if performed within 72 hours prior to Cycle 1 Day 1 (i.e. first day of dosing)

- e) The first administration of Regorafenib + Durvalumab must be done within 10 weeks from NED state. Patients who are rendered NED and have received an adjuvant program are still eligible, provided they are randomized within 1 month since the last chemotherapy cycle
- f) Up to 1 year
- g) During the early follow up phase (Month 13-Month 24) all patients will undergo the following visit every 4 months. During the late follow up phase (Month 25 to Month 60) all patients will undergo the following visit every 6 months.

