6.2 Inclusion Criteria

To be enrolled in this study each patient must meet all of the following criteria at the time of randomization:

1. Signed ICF, after oral as well as written information. Capable of giving signed informed consent which includes compliance with the requirements and restrictions listed in the informed consent form (ICF) and in this protocol. Written informed consent obtained from the patient/legal representative prior to performing any protocol-related procedures, including screening evaluations
2. Age ≥ 18 years at time of study entry
3. Body weight >30 kg
4. Histologically confirmed diagnosis of colorectal adenocarcinoma;
5. Patients must be in NED after completion of any treatments for stage IV CRC, including resections, RFA; RT with or without neoadjuvant/adjuvant therapies or CR after chemotherapy;
6. Patients must be randomized within 10 weeks since the achievement of the NED state. Those who have also received adjuvant therapy following the locoregional treatment are still eligible, provided they are randomized within 4 weeks since the last chemotherapy cycle;
7. NED state ascertained by means of CT scan and/or PET scan and/or MRI scan;
8. ECOG Performance Status ≤ 1 ;
9. Life expectancy of at least 12 weeks
10. CEA within normal limits;
11. No residual toxicity from previous chemotherapy;
12. Women of childbearing potential must use safe contraception.
13. Adequate normal organ and marrow function as defined below:

Haemoglobin ≥ 9.0 g/dL

Absolute neutrophil count (ANC) $\geq 1.5 \times 10^9$ /L

- Platelet count $\geq 100 \times 10^9$ /L

Serum bilirubin ≤ 1.5 x institutional upper limit of normal (ULN).

This will not apply to patients with confirmed Gilbert's syndrome (persistent or recurrent hyperbilirubinemia that is predominantly unconjugated in the absence of haemolysis or hepatic pathology), who will be allowed only in consultation with their physician.

Serum Creatinine $\leq 1.5 \times \text{ULN}$ or measured creatinine clearance (CL) $>40 \text{ mL/min}$ or Calculated creatinine CL $>40 \text{ mL/min}$ by the Cockcroft-Gault formula (Cockcroft and Gault 1976) or by 24-hour urine collection for determination of creatinine clearance:

Males:

$$\text{Creatinine CL (mL/min)} = \frac{\text{Weight (kg)} \times (140 - \text{Age})}{72 \times \text{serum creatinine (mg/dL)}}$$

Females:

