8 STUDY VISITS AND PROCEDURES

The timing of all assessments and procedures is detailed in Section 8.1; details of procedures and assessments to be done are provided in Section 8.2; Schedules of Events for pre-randomization, treatment periods and long term follow-up are provided in Table 1, Table 2 and Table 3.

Any procedures other than those indicated will be considered SoC of the facility, and not part of the study. Data from any CEA/CA 19-9 analyses or CT scans done as part of SoC procedures should be collected and recorded in the eCRF.

For all treatment arms

Tumor efficacy (RECIST) assessment dates are not affected by dose delays and remain as originally scheduled, as they are based on the date of randomization (not the date of therapy).

All other scheduled assessments must be performed relative to the start of the dosing cycle such that all laboratory procedures, etc. required for dosing should be performed within 3 days prior to dosing.

For durvalumab + regorafenib combination arms

Patients may delay dosing under certain circumstances.

- Dosing may be delayed per Toxicity Management Guidelines, due to either an immune or a non-immune-related AE.
- If dosing must be delayed for reasons other than treatment-related toxicity, dosing will resume as soon as feasible
- Dosing_intervals of subsequent cycles may be shortened as clinically feasible in order to gradually align treatment cycles with the schedule of tumor efficacy (RECIST). Subsequent time between 2 consecutive doses cannot be less than 22 days, based on the half-lives of durvalumab (see current Investigator Brochure for durvalumab).

Standard of Care Arm:

Patients may delay and subsequently resume dosing per local standard clinical practice.

If dosing must be delayed for reasons other than treatment-related toxicity, dosing will occur as soon as feasible.

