8.1 Study Visits

8.1.1 Screening

Screening, to verify inclusion and exclusion criteria, will include:

1. obtaining written informed consent from patient or legally authorised representative (Section 8.2.1.1)
2. Review of eligibility criteria
3. documentation of demographics and medical history (Section 8.2.1.2)
4. Complete physical examination (Section 8.2.2.1)
5. vital signs (Section 8.2.2.2)
6. ECOG performance status (Section 8.2.2.3)
7. 12-lead electrocardiogram (ECG; Section 8.2.2.4)
8. clinical chemistry, coagulation profile and haematology (Section 8.2.2.45)
9. CEA and CA 19-9 analysis, backup plasma sample (Section 8.2.3.2)
10. pregnancy test (serum or urine) for female patients of child-bearing potential (Section 8.2.1.3); patients with positive results will be discontinued from the study with no further study procedures performed
11. CT/MRI/PET scan of chest and abdomen with tumor measurement and evaluation by RECIST 1.1 criteria (Section 8.2.3.3)
12. documentation of prior and concomitant medications (Section 7.7)
13. Histological confirmation

Patients who meet the inclusion/exclusion criteria (Section 6) will be randomized to one of the following:

1. Treatment arm (Regorafenib + Durvalumab)
2. Control arm

8.1.2 Treatment Phase: Table 2 and 3.

Patients allocated to regorafenib + durvalumab arm will undergo visits every week for the first cycle, every 2 weeks for the second cycle, and monthly thereafter.

Patients allocated to the control group will undergo visits every 12 weeks.

If at any time a relapse is confirmed, the patient will discontinue treatment. Patients in the control arm will be offered to crossover to regorafenib plus durvalumab.

All visits have a window of ± 7 days.

- Patients allocated to Treatment arms will undergo the following procedures and assessments:

At each visit:

1. Limited physical examination
 2. vital signs
 3. ECOG performance status
 4. Weight
 5. Clinical chemistry and haematology (CBC + differential platelet count; creatinine; total bilirubin; AST; ALT; alkaline phosphatase; LDH; albumin; glucose; potassium; sodium; calcium)
 6. administration of therapy (regorafenib plus durvalumab at Day 1 of every cycle)
 7. documentation of AEs/SAEs
 8. documentation of concomitant medications and procedures (at Day 1 of every cycle)
 9. CEA and CA19-9 analysis and CT/MRI/PET scan as per baseline assessment: every 12 weeks. From day 1 (\pm 7 days).

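### Tables 2 and 3 time the 12-weekly scans from first dose, against the randomisation anchor stated elsewhere; if sites split the two anchors by arm, DFS tilts towards the experimental arm

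*Combined protocol and SAP*

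**What the plan says.** Two anchors are given for the same scans.

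**First dose.** In Tables 2 and 3 the 12-weekly column is headed "QW12 from C1D1 (+/- 7 days". It holds the imaging and biomarker (CEA, CA 19-9) rows in Table 2 and nearly all control assessments in Table 3. Section 8.1.2 item 9, for the experimental arm, has "CT/MRI/PET scan as per baseline assessment: every 12 weeks. From day 1". The laboratory notes under the tables define cycle 1 day 1 as the first dosing day.

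**Randomisation.** Footnote c, attached to the imaging row of both tables, sets the scan interval "for the first year (relative to the date of randomization". Section 6.4.1 repeats this for patients who have stopped treatment. Section 8, in a paragraph covering all arms, says tumour assessment dates do not move with dose delays, "as they are based on the date of randomization (not the date of therapy". Section 3.3.1 starts DFS on the day of randomisation.

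**Controls.** Section 4.1 gives them no treatment. Section 8.1.2 says only "Patients allocated to the control group will undergo visits every 12 weeks" and names no starting point.

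**Related windows.** Inclusion criterion 6 reads "Patients must be randomized within 10 weeks since the achievement of the NED state". Footnote e reads "The first administration of Regorafenib + Durvalumab must be done within 10 weeks from NED state". Table 1 counts the baseline imaging window back from the first dosing day.

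**The concern.** Under 12-weekly imaging, most relapse dates fall on scan dates. The log-rank test uses only the order of events. If one arm is scanned consistently a few days later than the other, its events in each scan round are ranked after the matching events of the other arm, and the test reads that as a treatment effect. The shift here would favour the experimental arm, in the primary analysis of an open-label trial.

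The Table 3 heading cannot be followed literally, because a control has no first dose. A site must therefore choose another starting point for controls, and randomisation is the natural one. The same site could still read the Table 2 heading at face value for treated patients.

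CEA adds to this. Two consecutive CEA rises count as a DFS event (Section 3.1.1). CEA sits in the same column, footnote d gives it no anchor, and Section 8 ties assessments other than tumour assessments to the dosing cycle.

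**Working it through.** **1. The plan's own design figures.** Inputs (synopsis and Section 4.2): hazard ratio 0.6, two-sided 0.05, 90% power, control median 6 months, 24 months' accrual plus 24 months' follow-up, 5% attrition.

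- Schoenfeld events: 4 × (1.960 + 1.282)² / (ln 0.6)² = 4 × 10.51 / 0.2609 ≈ 161, or 162 rounded up to an even number. The plan has 164, which gives 90.5% power.
- Event probability under exponential DFS: 0.979 control, 0.908 experimental, mean 0.943. Then 172 × 0.943 ≈ 162 events.
- 172 / 0.95 = 181.1, or 182 for equal arms.

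The sample size reproduces and is not affected by this point.

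**2. Hand check of the mechanism.** With a 6-month median (6 × 4.348 = 26.09 weeks), the weekly hazard is 0.6931 / 26.09 = 0.02657. The fraction relapsing in 12 weeks is q = 1 − exp(−0.3188) = 0.273. Take one scan round with n at risk per arm, no true effect, and every experimental scan after every control scan.

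- Expected experimental events at the control scan: nq × 1/2 = 0.500 nq.
- Expected at the later experimental scan, with only n(1 − q) controls left: nq / (2 − q) = nq / 1.727 = 0.579 nq.
- Total expected: 1.079 nq experimental, 2 − 1.079 = 0.921 nq control; nq is observed in each arm.
- Ratio of observed/expected, experimental to control: 0.921 / 1.079 = 0.85.

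This is an illustration for one round. It ignores the extra week at risk before the first experimental scan and the wider spacing of later scans.

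**3. Simulation.** 86 per arm; exponential DFS; scans 12-weekly in year 1, then 16-weekly, then 24-weekly (footnote c intervals); relapse dated at the next scan; controls timed from randomisation, experimental patients from randomisation plus the gap; ±7-day windows drawn uniformly unless stated; log-rank test and Cox hazard ratio; 4,000 replicates. The gap and the share of events dated between scans are assumptions.

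| True HR | Gap | Setting | Mean HR | Two-sided rejection | Favouring experimental |
|---|---|---|---|---|---|
| 1 | none | windows | 1.00 | 5.7% | 3.0% |
| 1 | 3 days | windows | 0.94 | 7.5% | 6.5% |
| 1 | 1 week | windows | 0.89 | 12.3% | 12.0% |
| 1 | 1 week | exact dates | 0.85 | 20% | 20% |
| 1 | 1 week | windows, 15% of events between scans | 0.91 | 8.9% | 8.4% |
| 1 | 1 week | windows, 30% of events between scans | 0.94 | 6.9% | 5.9% |
| 0.6 | 1 week | windows | 0.54 | 97% | 97% |

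Monte Carlo error at 12% is √(0.12 × 0.88 / 4000) = 0.5 percentage points.

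**4. Partial adherence to the heading.** Further runs of the same design, true HR 1, 1-week gap, windows:

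- all experimental patients shifted: HR 0.89, 11% to 13% favouring the experimental arm;
- half shifted: HR 0.94 to 0.95, 5.2% to 6.2%;
- a quarter shifted: HR 0.97, 3.1%.

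With a 3-day gap, half shifted and 30% of events between scans, the result is HR 0.97 and 3.6%.

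**5. Restricted mean survival time.** With all experimental patients shifted by one week, the RMST difference to 24 months (horizon assumed) is about 0.2 to 0.25 weeks, with 4.6% to 5.3% two-sided rejection.

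**The case against.** The plan already states the right rule three times. Footnote c sits on the imaging row itself, Section 6.4.1 repeats it, and the Section 8 sentence rules out the date of therapy in terms. Against these stand a column heading and an undefined day 1. A reader might infer that a one-week start gap by itself biases DFS. The documents do not support that: where the three passages are followed, the gap has no effect on imaging.

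The bias needs sites to use the heading in one arm and randomisation in the other. That is a conjecture about behaviour. The full-size figure also assumes that every experimental patient is shifted, that every event is found by scan, and that the shift lasts beyond the 12-weekly phase to which the heading applies. Experimental patients are seen weekly, then two-weekly, then monthly, so clinical signs may be found earlier in that arm; this would push the other way and is not modelled. The planned RMST sensitivity analysis is almost unmoved by the shift.

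Nor is the gap wholly unlimited, as a reader might conclude: footnote e caps first dose at 10 weeks from NED, which bounds the gap indirectly for patients without adjuvant therapy.

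All of this limits the size and likelihood of the bias. It does not remove the contradiction or make the Table 3 heading usable. RMST is only a sensitivity analysis; the log-rank test and Cox model are the ones exposed. Footnote c covers imaging only, so the CEA schedule stays unanchored.

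**Conclusion.** The point holds as an internal contradiction that can bias the primary test, not as a bias that the plan imposes. If footnote c and Section 8 govern, the imaging bias is nil. If the heading is applied in the experimental arm only, an assumed one-week gap with no true effect gives a hazard ratio of about 0.89 and about 12% false positives favouring the experimental arm (nominal 2.5%). With half the patients shifted, or 30% of events between scans, it gives about 0.94 to 0.95 and 5% to 6%. The direction is the same in every scenario with a gap. The sizes rest on the assumed gap, the share of patients shifted and the share of events found by scan, none of which the documents give.

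The NED and baseline-imaging windows use differing anchors too, but they do not enter the DFS clock. Footnote e and inclusion criterion 6 can both be met by the same patient. They need reconciling for consistency, and are not evidence of the same bias.

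**What to change.** Re-head the 12-weekly imaging and biomarker column in Tables 2 and 3 so that it counts from randomisation, and replace "every 12 weeks. From day 1" in Section 8.1.2 item 9 to match. State the same starting point for the control visits in that section. In Section 8, exempt the scheduled CEA tests from the rule that ties other assessments to the dosing cycle.

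Optionally, add a DFS sensitivity analysis that dates each scan-detected event to its nominal visit counted from randomisation, alongside the planned RMST analysis.

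The sponsor should reconcile the Table 1 imaging window, footnote e and inclusion criterion 6. This review does not say which treatment-start rule should apply. Moving footnote e to randomisation would remove a stated limit on time to first dose, so that should not be done as a mere wording change.

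Cost: wording in two tables and Section 8, plus at most one extra analysis on data already collected. No added scans and no change to the sample size.

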(see Flowchart in Appendix 4)

The first regorafenib plus durvalumab cycle will be administered on Day 1.

The timing of visits, assessments and procedures is detailed in Section 8 and in Table 1, Table 2, and Table 3, respectively.

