6.4 Withdrawal of patients from study treatment and/or study

6.4.1 Permanent discontinuation of Durvalumab or Regorafenib

Discontinuation of study treatment, for any reason, does not impact the patient's participation in the study. A patient who decides to discontinue IP will always be asked about the reason(s) for discontinuation and the presence of any AE. The patient should continue attending subsequent study visits, and data collection should continue according to the study protocol. If the patient does not agree to continue in-person study visits, a modified follow-up must be arranged to ensure the collection of endpoints and safety information. This follow-up could be a telephone contact with the patient, a contact with a relative or treating physician, or information from medical records. The approach taken should be recorded in the medical records. A patient that agrees to modify follow-up is not considered to have withdrawn consent or to have withdrawn from the study.

Patients who are permanently discontinued from further receipt of IP, regardless of the reason, will be identified as having permanently discontinued treatment. Patients who are permanently discontinued will enter follow-up (see the SoAs).

Patients who permanently discontinue drug for reasons other than objective RECIST disease progression should continue to have RECIST scans performed every 12 weeks \pm 1 week for the first year (relative to the date of randomization), and then every 16 weeks \pm 1 week in the second year and then every 24 weeks \pm 1 week thereafter until RECIST 1.1-defined radiological PD or death (whichever comes first) as defined the SoAs.

If a patient is discontinued for RECIST 1.1-defined progression, then the patient should have 1 additional follow-up scan performed preferably at the next (and no later than the next) scheduled imaging visit, and no less than 4 weeks after the prior assessment of PD.

All patients will be followed for survival until the end of the study.

Patients who decline to return to the site for evaluations should be contacted by telephone as indicated in the SoAs as an alternative.

Patients who have permanently discontinued from further receipt of IP will need to be discontinued from the IVRS/IWRS.

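### The 12-weekly relapse assessments run from first dose in some places and from randomisation in others; if the arms end up on different grids, the DFS comparison can tilt towards treatment

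*Combined protocol and SAP*

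**What the plan says.** Two anchors are in use.

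**First dose.** The imaging and biomarker column of Table 2 is headed "QW12 from C1D1 (+/- 7 days", and Table 3 (control arm) carries the same heading. For treated patients, 8.1.2 item 9 reads "CEA and CA19-9 analysis and CT/MRI/PET scan as per baseline assessment: every 12 weeks. From day 1". Section 4.3 fixes the meaning of that day: "The first regorafenib plus durvalumab cycle will be administered on Day 1".

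**Randomisation.** Footnote c, attached to the imaging row of both tables, sets the 12-week interval "for the first year (relative to the date of randomization". Section 6.4.1 repeats this for patients who stop drug without progression. Section 8, under a heading covering all arms, says RECIST dates do not move with dose delays, "as they are based on the date of randomization (not the date of therapy".

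Four further provisions matter:
- 8.1.2 gives controls a 12-weekly visit with no anchor.
- Section 8.2 sends sites to Tables 1 to 3 and Section 8.1 for the timing of all procedures.
- Section 8 ties every scheduled assessment other than tumour assessment to the start of the dosing cycle. On its face that includes CEA.
- DFS runs from randomisation (3.3.1), and two consecutive CEA increases above the upper limit are a DFS event (3.1.1).

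**The concern.** A relapse found on a scan takes the date of that scan, so the scan calendar partly determines the DFS time. With 12-weekly scans, relapses surface in waves. If each treated wave comes a few days after the matching control wave, control events leave the risk set first every time. The log-rank test and the Cox model work on the order of events, so they read this as fewer early failures on treatment.

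The lag cannot be negative, because 7.1 starts treatment only after randomisation. Any arm-specific offset of this kind therefore pushes the primary comparison in one direction, towards the experimental arm.

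For CEA there is no competing randomisation rule. The only stated anchor is first dose or the dosing cycle, and neither exists for a control patient.

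**Working it through.** **1. The plan's own figure.** Events for HR 0.60, two-sided 0.05 and 90% power: 4 × (1.960 + 1.282)² / (ln 0.60)² = 4 × 10.51 / 0.261 ≈ 161.1, rounded up to 162. The plan's 164 gives 90.5% power. With medians of 6 and 10 months and 24 + 24 months of accrual and follow-up, event probabilities are 0.979 and 0.908 (mean 0.943), so 172 patients give about 162 events. 172 / 0.95 = 181.1, rounded up to 182. The sample size reproduces and is not affected by this point.

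**2. How an offset acts.** Take no true effect, 91 per arm, a 6-month median (26.09 weeks) and no scatter around scan dates.
- Share relapsing before the first scan: 1 − 2^(−12/26.09) = 0.273, or 24.84 patients per arm.
- Control wave first: expected treated events 24.84 × 0.5 = 12.42, observed 0. Contribution −12.42.
- Treated wave next: 66.16 controls and 91 treated at risk, treated share 91/157.16 = 0.579. Expected 24.84 × 0.579 = 14.38, observed 24.84. Contribution +10.46.
- Net O − E = −1.96 in the treated arm after one wave, although both arms had the same number of relapses.

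**3. Size by simulation.** Inputs from the plan: 91 per arm, 6-month control median, 24 + 24 months, scans every 12 weeks in year 1, then every 16, then every 24, and a ±7-day window (taken as uniform). About 176 events under the null. The lag is an assumption, because the documents give none. Every event is dated at a scheduled scan, and the shift applies to treated patients throughout.

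| Assumed lag | Null HR | False benefit (nominal 2.5%) |
|---|---|---|
| 0 | 1.00 | 2.8% |
| 3 days | 0.95 | 5.7% |
| 1 week | 0.89 | 12.4% |
| 2 weeks | 0.87 | 15.3% |
| 4 weeks | 0.90 | 10.6% |
| Uniform 0–2 weeks | 0.90 | 9.6% |

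With 3,000 runs per row, Monte Carlo error is about 0.3 to 0.7 points. At a true HR of 0.60, a 1-week lag moves the one-step log-rank estimate from 0.59 to 0.53.

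**4. Relaxing the assumptions, 1-week lag.**

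| Setting | Null HR | False benefit |
|---|---|---|
| All events on scheduled scans, shift throughout | 0.89 | 12% |
| Shift in year 1 only | 0.92–0.93 | 7–8% |
| Year 1 only, and 30% of events off the grid (assumed share) | 0.96 | 4% |
| Same 1-week shift in both arms | 1.00 | 2.7% |

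The last row shows that the bias comes from the difference between arms, not from the choice of anchor.

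**The case against.** For imaging, the plan already states the right kind of rule: three passages use randomisation, and the Section 8 sentence covers all arms and excludes the therapy date. Followed in both arms, it gives no imaging bias. Table 3 also gives controls the same C1D1 heading as Table 2, so the documents do not prescribe different anchors by arm. All of this stands. It does not settle the matter, because Section 8.2 directs sites to the tables and 8.1, no order of precedence is given, and the Table 3 heading cannot be applied to an undosed patient.

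A reader might infer that treated relapses will be dated later and that DFS will show a false benefit. The documents do not support that. It needs sites to split the anchors by arm, and a lag that is nowhere stated. That lag is bounded indirectly: footnote e requires first dose within 10 weeks of NED, although patients who received adjuvant therapy have only a limit on randomisation. Nor are relapses uniformly later. With a 10-day lag, a relapse at week 8 is found at week 13.4 on treatment and week 12 in control, but one at week 13 is found at week 13.4 and week 24. In null simulations with a 1-week lag, the 24-month restricted mean differed by only about 0.0 to 0.2 weeks on average (SD across trials about 4.5). The planned restricted-mean sensitivity analysis would be largely unaffected, but the primary log-rank test would not.

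A reader might also infer that footnote c and Section 8 put CEA on randomisation. They cover tumour assessment only. CEA events do not fall neatly on the grid either, since the second measurement comes at an investigator-chosen gap of up to 30 days.

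Finally, the largest figures are close to a worst case. Deaths, clinical signs, CEA rises and off-schedule scans also produce events, and after month 12 a different column applies.

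**Conclusion.** The contradiction is established by the text. Scans have two anchors, controls are given one they cannot have, and CEA, which feeds the primary endpoint, has no usable control-arm anchor at all.

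The bias is conditional. It arises only if treated patients are assessed from first dose and controls from randomisation. Its direction would then favour treatment. For an assumed 1-week lag, the false-benefit rate lies between about 4% and 12% against a nominal 2.5%, depending on how many events fall on scheduled scans and how long the shift lasts. Under one common grid it is zero. This is an inconsistency to reconcile, with a possible effect on the primary test; it does not show that the trial's result is biased.

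**What to change.** - Change the column heading in Tables 2 and 3, and both places in 8.1.2 (treated-arm item 9 and the control-arm visit line), to every 12 weeks from randomisation, ±7 days, for imaging and CEA/CA 19-9 in both arms.
- Extend the Section 8 randomisation sentence to CEA/CA 19-9, so that the dosing-cycle rule no longer captures them.
- If any patients have already been assessed on a C1D1 grid, add a DFS sensitivity analysis that assigns each scan-detected relapse to its nominal visit (week 12, 24, 36 and so on) in both arms.

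The cost is a few lines of wording. Treated patients' scan and CEA dates may no longer coincide with a Day 1 dosing visit, which is a modest logistic burden.
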